## **OVERALL SUMMARY**

Non-invasive and effective treatments are much needed for the cure of dementia. Available treatments, however, are mainly symptomatic and their mechanism of action is largely unrelated to disease pathophysiology. Intermediate phenotypes can bridge the gap between pathology and clinical symptoms. Targeting these biomarkers might represent a biologically-sound and effective treatment approach. Increasing evidence suggests that the disruption of large-scale networks might provide the missing link between pathology and clinical symptoms in several neurodegenerative dementias. This pilot project will test a non-invasive approach to restore large-scale networks connectivity in two neurodegenerative disorders in which pathology has been clearly linked to large-scale network disruption, i.e. Alzheimer's disease (AD) and behavioural frontotemporal dementia (bvFTD). The effect of network stimulation on the clinical symptoms, as well as on brain connectivity, will be tested.

### **A. Background and State of Art**

Resting-state fMRI studies have shown that Alzheimer's disease (AD) is associated with the progressive degeneration of the default mode network (DMN), and behavioural frontotemporal dementia (bvFTD) with salience network (SN) degeneration (Pievani et al, 2011a). These 2 diseases also feature anti-correlated patterns (DMN connectivity is reduced and SN is hyper-activated in AD, while the opposite is seen in bvFTD; Zhou et al, 2010). Although DMN and SN disruption offer an attractive target for AD and bvFTD treatment, no study has investigated the efficacy of recalibrating these networks. Repetitive transcranial direct current stimulation (tDCS) and transcranial magnetic stimulation are non-invasive techniques capable to restore brain function through direct stimulation of disrupted networks or indirect suppression of hyper-activated networks (Cotelli et al, 2011; Naeser et al, 2005). In this pilot project we will test the efficacy of DMN and SN recalibration in AD and bvFTD through tDCS.

### **B. Hypothesis and Specific Aims**

#### **a. Hypothesis and significant**

Neurodegenerative disorders disrupt large-scale neuronal networks. Modulating disease-specific networks might provide an effective approach to restore network function and improve clinical symptoms.

#### **b. Specific Aims**

- 1) To assess the clinical/cognitive effect of disease-specific networks stimulation in AD (DMN stimulation) and bvFTD (SN stimulation);
- 2) To assess the clinical/cognitive effect of anti-correlated networks suppression in AD (SN suppression) and bvFTD (DMN suppression);
- 3) To investigate correlations between tDCS-related network changes and biomarker changes in AD and bvFTD.

#### **c. Experimental design**

##### **Aim 1**

##### **Population study**

Twenty patients (10 mild AD and 10 mild bvFTD) will be recruited at the IRCCS-Fatebenefratelli of Brescia. Inclusion criteria will be a diagnosis of AD or bvFTD according to the current clinical criteria (Albert et al., 2011; Rascovsky et al., 2011) and ability to provide written informed consent. Exclusion criteria will be moderate/severe dementia (MMSE<18) and/or the presence of any medical or psychiatric illness that could interfere in completing assessments.

### **Paradigm 1 - direct stimulation of disconnected networks**

The DMN is anchored to `posterior` regions and the SN is anchored to `anterior` regions (Zhou et al., 2010). DMN connectivity will be stimulated in AD patients through anodal tDCS of the posterior DMN; SN connectivity will be stimulated in bvFTD patients through anodal tDCS of the anterior SN.

#### **Clinical assessment**

Each patient will undergo a clinical and neuropsychological evaluation to assess symptoms and cognition at baseline (before tDCS session, T0) and follow-up (after the tDCS sessions, T1; and 6 months after tDCS treatment, T2). Patients will also undergo biological samples collection (CSF at T0, blood samples at T0, T1, T2) to assess the effect of tDCS on inflammatory measures (optional sub-study).

#### **Outcome measures**

We will test whether the stimulation of AD- and bvFTD-disrupted networks improves patients clinical condition.

PRIMARY efficacy parameters will be:

- change in scores at T1 compared with T0 for clinical and behavioural scores in AD and bvFTD patients

SECONDARY outcome measures will be:

- change in scores at T1 compared with T0 for cognitive performance in AD and bvFTD patients
- change in scores at T2 compared with T0 for clinical, behavioural, and cognitive performance in AD and bvFTD patients

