### **Aim2**

DMN and SN feature a divergent pattern of connectivity in AD and bvFTD patients (Zhou et al., 2010). These anti-correlated networks offer an alternative approach to recalibrate network connectivity: low-frequency/cathodal stimulation can indeed be used to inhibit hyper-activated networks and improve clinical conditions (Naeser et al., 2005; Martin et al., 2004). We will therefore test whether inhibition of AD- and bvFTD-hyper-activated networks improves clinical condition. The experimental design of this task is analogous to that of AIM1, the key difference being the administration of cathodal tDCS to suppress hyper-activated networks.

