#### **Outcome measures**

We will test whether the suppression of AD and bvFTD anti-correlated networks improves clinical condition.

PRIMARY and SECONDARY efficacy parameters will be the same as in AIM1.

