### **Statistical analysis**

Sample size for this pilot study (n=10 subjects for each experimental group) has been determined on the basis of previous tDCS (Cotelli et al., 2011) and rs-fMRI studies (Lorenzi et al., 2011; Pievani et al., Alzheimer's Dementia 2014) of the Consortium.

Paired t-tests will be used to compare pre-treatment (T0) *versus* post-treatment (T1, and T2) variables in each treatment group (AD and bvFTD).

Correlations between clinical/cognitive changes and imaging biomarkers will be assessed with Pearson's correlation coefficient.

Two-sample t-tests will be used for cross-sectional comparisons of clinical/cognitive scores between paradigm 1 and 2 (i.e. network stimulation *versus* network inhibition) in the experimental groups and to evaluate differences in clinical, cognitive, and neuroimaging measures between the experimental groups and controls at baseline.

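### The plan words its aims as tests of tDCS efficacy, but the primary analysis is uncontrolled before-after change, and the one treatment contrast has no stated allocation method, time point or T0 adjustment

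*Combined protocol and SAP*

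**What the plan says.** The causal wording runs through the plan.

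- Overall Summary: "The effect of network stimulation on the clinical symptoms, as well as on brain connectivity, will be tested".
- Section A: "In this pilot project we will test the efficacy of DMN and SN recalibration in AD and bvFTD through tDCS".
- Specific Aims: "To assess the clinical/cognitive effect of disease-specific networks stimulation in AD (DMN stimulation) and bvFTD (SN stimulation".
- Aim 1, Outcome measures: "We will test whether the stimulation of AD- and bvFTD-disrupted networks improves patients clinical condition".
- Aim 2: "We will therefore test whether inhibition of AD- and bvFTD-hyper-activated networks improves clinical condition", and again under its Outcome measures, "We will test whether the suppression of AD and bvFTD anti-correlated networks improves clinical condition".
- Aim 1, Clinical assessment, on blood and CSF samples: "to assess the effect of tDCS on inflammatory measures (optional sub-study".

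The primary parameter is the T1-versus-T0 change in clinical and behavioural scores. Under Statistical analysis, "Paired t-tests will be used to compare pre-treatment (T0" with T1 and T2, within each treatment group. Paradigm 1 is anodal and paradigm 2 cathodal; no sham, untreated or waiting-list patient arm appears. The Control group section describes 20 healthy people assessed at baseline.

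The same Statistical analysis section plans two-sample t-tests for a cross-sectional comparison of clinical and cognitive scores between the two paradigms. It names neither a time point nor a covariate. The population paragraphs for Aims 1 and 2 each describe recruitment of 10 AD and 10 bvFTD patients, but not how a patient comes to receive one paradigm rather than the other.

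**The concern.** The question asked and the analysis planned do not match. A paired change at T1 mixes any effect of tDCS with expectancy, retest effects, regression to the mean and, for clinician- or informant-rated scales, knowledge that treatment was given. At T2, six months on, expected decline works the other way and could hide a benefit. No concurrent patient group separates these from tDCS. A significant T1 improvement could therefore be reported as efficacy when none exists.

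The paradigm 1 versus 2 contrast within a disease is the one comparison that could be made causal, in a relative sense. As written, it appears to leave the T0 scores unused. If allocation is not random, a difference already present at T0 could be taken for a difference between paradigms.

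**Working it through.** **1. The plan's own figure.** The only design figure is n=10 per experimental group, justified by reference to earlier studies. The documents give no alpha, power, effect size, SD, T0-T1 correlation or dropout rate, so it cannot be reproduced and is not called wrong. Everything below assumes a two-sided 0.05 test and is illustrative.

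**2. Which n applies to the paired test.** Statistical analysis gives n=10 per experimental group, but describes the treatment groups as AD and bvFTD. The paired tests could be run per paradigm (n=10) or pooled over paradigms within a disease (n=20). Both are shown.

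**3. Paired test with no tDCS effect.** Let the non-specific shift be s, in SDs of the change score. The chance of a significant improvement is P[T > t(0.975, n-1)], where T is noncentral t with n-1 df and noncentrality s*sqrt(n). The critical values are 2.262 (n=10) and 2.093 (n=20).

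| s (assumed) | n=10 | n=20 |
|---|---|---|
| 0 | 2.5% | 2.5% |
| 0.2 | 8% | 13% |
| 0.3 | 13% | 25% |
| 0.5 | 29% | 56% |

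The 95% CI half-width is 2.262/sqrt(10) = 0.72 SD of change at n=10 and 2.093/sqrt(20) = 0.47 at n=20. A larger n makes a false attribution more likely, because the test detects the non-specific shift more reliably.

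**4. Paradigm 1 versus 2, 10 per arm, as planned.** The two-sample t-test has 18 df. It reaches 80% power at 1.32 score SD, with half-width 2.101*sqrt(2/10) = 0.94 score SD.

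**5. The same contrast with ANCOVA on T0.** The residual SD is sqrt(1-r^2) score SD, with 17 df. Before chance T0 imbalance is allowed for, 80% power needs 1.330*sqrt(1-r^2): 1.15, 0.95 and 0.58 at r = 0.5, 0.7 and 0.9. Those figures are slightly optimistic. Simulated trials (bivariate normal, chance imbalance included) give about 78% power at those differences. The simulated requirements are:

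| r (assumed) | Difference for 80% power, score SD | 95% CI half-width, score SD |
|---|---|---|
| planned test, any r | 1.32 | 0.94 |
| 0.5 | about 1.18 | about 0.83 |
| 0.7 | about 0.98 | about 0.68 |
| 0.9 | 0.59-0.60 | about 0.42 |

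At r = 0.2 ANCOVA needs about 1.34, marginally more than the planned test; at r = 0.3 about 1.30. There is almost no gain at such correlations.

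**6. Systematic T0 difference.** With no true paradigm difference but T0 means assumed 0.5 SD apart, simulation gives an unadjusted T1 comparison a false-positive rate of 8%, 12% and 16% at r = 0.5, 0.7 and 0.9. ANCOVA stays near 5%, given a common linear relation of T1 to T0. Under random allocation the unadjusted test is unbiased, merely less precise, although a chance T0 difference above 0.5 SD would still arise in 26% of trials for any one score (SE = sqrt(2/10) = 0.447 SD).

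**The case against.** **It is a pilot, and the complaint is about wording.** The study is labelled a pilot, an uncontrolled pilot is legitimate, and the paired t-test is valid for the stated parameter, change from T0 to T1. All of that stands. A reader might infer that the design is invalid or that a sham arm is mandatory; the documents do not support that for a pilot. The aims and expectations are also not decision rules. What remains is that efficacy wording, and the reference to disease-modifying treatments in section C, go beyond what the analysis can show.

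**The contrast fix does not cure the primary test.** Correct. Both paradigms are active and differ in polarity and site within each disease, so a shared benefit cancels. Nor is the contrast listed as a primary or secondary outcome. The two parts of the fix address separate defects.

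**T0 handling and allocation are silent, not wrong.** A reader might infer that the trial is non-randomised and that T0 is definitely ignored. Neither is established. Part of the document was removed before review, so absence of an allocation method holds for the supplied text only. The contrast sentence names no time point, and it goes on to baseline comparisons with controls, so a T0 comparability check is possible. An unadjusted post-treatment comparison is only the natural reading.

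**The planned test is not the least precise option.** Also correct. Below r = 0.5 a change-score test is worse: at r = 0.3 it needs 1.325*sqrt(2*0.7) = 1.57 score SD against 1.32.

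**Correlations with imaging link clinical change to network change.** They are useful for mechanism, but the imaging measures are also before-after changes, so the correlations cannot replace a concurrent comparison.

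**Conclusion.** The concern holds in this form. The primary analysis can estimate change after tDCS but cannot attribute it to tDCS. This conclusion rests on the design alone and needs no assumed number. The paradigm 1 versus 2 contrast is under-specified (allocation, time point, T0 handling) and would usually gain from T0 adjustment.

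The sizes depend on assumptions. The attribution risk is 8% to 29% at n=10, or 13% to 56% at n=20, for assumed shifts of 0.2 to 0.5 SD of change. The gain from ANCOVA ranges from almost nothing at correlations of 0.2-0.3 to a detectable difference of 0.59-0.60 instead of 1.32 score SD at 0.9. Even then the contrast remains imprecise and speaks only to relative efficacy. The matter should be fixed, but it does not invalidate the pilot.

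**What to change.** 1. **Allocation.** Allocate patients at random to paradigm within each disease. Section G has both paradigms starting in Month 1, so this is feasible. For patients already allocated, state how, and report their contrast as non-randomised. If allocation is already random, say so.
2. **Contrast.** In Statistical analysis, replace the paradigm 1 versus 2 t-test with an ANCOVA of T1 (and T2) scores on paradigm, adjusted for T0, within each disease, with 95% CI. Report it as relative efficacy only.
3. **Paired changes.** Report them as estimates with 95% CI, and state whether they are per paradigm (n=10) or pooled per disease (n=20).
4. **Interpretation.** Describe the paired results as before-after change in a pilot, not as efficacy or disease modification, and align the summary, aims, outcome, expectation and significance text. A claim that tDCS works would need a concurrent randomised inactive comparison, which is not requested here.

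The cost is a randomisation list per disease, one changed analysis sentence using data already collected, one degree of freedom (17 instead of 18) and wording edits. No patients or visits are added. The price is more modest claims and a between-paradigm estimate that says nothing about absolute benefit.

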### **Aim2**

DMN and SN feature a divergent pattern of connectivity in AD and bvFTD patients (Zhou et al., 2010). These anti-correlated networks offer an alternative approach to recalibrate network connectivity: low-frequency/cathodal stimulation can indeed be used to inhibit hyper-activated networks and improve clinical conditions (Naeser et al., 2005; Martin et al., 2004). We will therefore test whether inhibition of AD- and bvFTD-hyper-activated networks improves clinical condition. The experimental design of this task is analogous to that of AIM1, the key difference being the administration of cathodal tDCS to suppress hyper-activated networks.

#### **Population study and clinical assessment**

Ten mild AD and 10 mild bvFTD patients will be recruited and assessed following the procedures and inclusion/exclusion criteria described in AIM1. Patients will be evaluated at baseline (T0), after tDCS sessions (T1), and after 6 months (T2).

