### **Aim3**

To elucidate the mechanisms underlying network recalibration, in vivo biomarkers of structural and functional networks connectivity will be collected off-line. Each subjects will undergo an MRI scan on a 3T scanner at the UO3. The following sequences will be collected:

- resting-state functional MRI (rs-fMRI), to assess DMN and SN functional connectivity
- arterial spin labelling (ASL), to measure DMN and SN brain perfusion
- diffusion tensor imaging (DTI), to measure DMN and SN structural connectivity
- structural MRI, for the routine assessment of cortical and hippocampal atrophy

Scan will be collected at baseline (T0, prior to tDCS experiment), after completion of the tDCS sessions (T1), and after 6 months (T2). The subjects included in this analysis will be those recruited for AIM1 and AIM2 (20 AD and 20 bvFTD).

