### **G. Milestone Mo 18**

**M1:** Successful implementation of the clinical study (First 2 patients completing T0 assessment; Month 1)

**M2:** Successful implementation of paradigm 1 (First patient completing tDCS sessions; Month 1)

**M3:** Successful implementation of paradigm 2 (First patient completing tDCS sessions; Month 1)

**M4:** Successful implementation of the longitudinal study (First patient completing T1 assessment; Month 2)

**M5:** Successful implementation of the longitudinal study (First patient completing T2 assessment; Month 8)

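### No rule is described for assigning an eligible patient to Paradigm 1 or Paradigm 2, so the planned unadjusted comparison of the two paradigms is open to selection bias

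*Combined protocol and SAP*

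**What the plan says.** The combined protocol and SAP sets up two parallel sets of patients.

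- Aim 1, Population study: "Twenty patients (10 mild AD and 10 mild bvFTD) will be recruited at the IRCCS-Fatebenefratelli of Brescia". These patients receive Paradigm 1.
- Aim 2, under its own recruitment heading, reads: "Ten mild AD and 10 mild bvFTD patients will be recruited and assessed following the procedures and inclusion/exclusion criteria described in AIM1". These patients receive Paradigm 2.
- Aim 3 confirms that the two sets are different people: "The subjects included in this analysis will be those recruited for AIM1 and AIM2 (20 AD and 20 bvFTD").
- Section G sets the same first-patient target for each paradigm: "Successful implementation of paradigm 1 (First patient completing tDCS sessions; Month 1") and "Successful implementation of paradigm 2 (First patient completing tDCS sessions; Month 1"). Section F gives a single window, Months 1-29, for all tDCS sessions.
- Section B.e, Statistical analysis: "Two-sample t-tests will be used for cross-sectional comparisons of clinical/cognitive scores between paradigm 1 and 2". The sentence explains this as stimulation against inhibition. It names no visit and no covariate.

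The primary efficacy parameter, used for both aims, is a within-patient change: "change in scores at T1 compared with T0 for clinical and behavioural scores in AD and bvFTD patients".

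The text available for review mentions no randomisation, alternation, matching, stratification, order of filling or concealment. Some front matter was not available.

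**The concern.** Two patients with the same diagnosis who meet the same criteria may receive different paradigms, and the plan does not say what decides this. If staff decide, milder, more cooperative or more promising patients may collect in one group without anyone intending it. The paradigms are then compared on scores that are not corrected for where each group started, so any such difference passes into the result.

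This is the only contrast in the plan between two treated groups. It would be read as showing whether stimulating the disrupted network works better or worse than suppressing the anti-correlated one. The paired T0 v T1 tests make no comparison between paradigms, so allocation does not affect them.

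**Working it through.** **Structure.** 10 AD + 10 bvFTD (Aim 1) plus 10 AD + 10 bvFTD (Aim 2) gives 4 x 10 = 40 patients, or 20 per diagnosis, as stated under Aim 3. Each patient therefore receives one paradigm only, and the comparison is between patients, with 10 v 10 within a diagnosis. The plan gives no figure for this comparison that could be reproduced.

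**Assumptions for the illustration** (none is in the documents): two-sided 5% test; no true paradigm effect; equal SDs; baseline difference between the groups of d = 0.25, 0.5 or 1.0 SD; T0-T1 correlation 0.7 where needed.

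**1. The planned raw t-test, with the difference carried fully into the compared score.** Degrees of freedom are 10 + 10 - 2 = 18. The noncentrality is d x sqrt(10 x 10 / 20) = 2.236 d, that is 0.559, 1.118 and 2.236. The critical value is 2.101. The noncentral t distribution gives the first row of the table below. If the diagnoses were pooled (20 v 20, which the text does not exclude), the rates would be 12.0%, 33.8% and 86.9%.

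**2. The same test, with the difference reaching T1 only through the T0 score.** The shift at T1 is 0.7 d, that is 0.175, 0.35 and 0.7 SD. Simulation with 40,000 trials per case gives the second row.

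**3. ANCOVA of T1 on T0, with the difference carried fully.** Adjustment removes 0.7 d and leaves 0.3 d. Simulation gives the third row. At d = 1.0 the rate is 18.7% if the correlation is 0.5 and 9.6% if it is 0.8.

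**4. t-test on change from T0.** With a fully carried difference the shift cancels. If the difference acts only through T0, a shift of (0.7 - 1) d = -0.3 d remains.

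| Analysis, 10 v 10, no true effect | 0.25 SD | 0.5 SD | 1.0 SD |
|---|---|---|---|
| Raw score, difference fully carried | 8.3% | 18.5% | 56.2% |
| Raw score, difference only through T0 | 6.8% | 11.4% | 31.7% |
| ANCOVA, difference fully carried | 5.6% | 7.1% | 12.1% |
| Change score, difference fully carried | about 5% | about 5% | about 5% |
| Change score, difference only through T0 | about 5% | about 7% | about 13% |

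With no baseline difference every method rejects in about 5%.

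**5. Under randomisation.** The expected difference is zero and the false-positive rate is 5%. With 10 per group the chance difference at T0 still has a 95% range of ±1.96 x sqrt(2/10) = ±0.88 SD, so adjustment for T0 remains useful.

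Each adjusted analysis holds its error rate only if its own assumption about the baseline difference is right. Neither protects against selection on prognosis that T0 does not capture. Adjustment reduces the problem but does not replace randomisation.

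**The case against.** There are five fair points on the other side.

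- **The comparison is minor within the plan.** It is not one of the three aims and is not listed as a primary or secondary outcome. The study is a pilot, and 10 v 10 has 80% power only for a difference of about 1.32 SD. This stands and limits the severity. It does not remove the point, because the test is planned.
- **The comparison may be a baseline check.** The word cross-sectional, with no visit named, allows this reading. However, the stimulation-against-inhibition explanation favours a treatment comparison, and the mention of baseline sits with the comparison against controls. The ambiguity is itself something to resolve.
- **The milestones do not name the diagnosis.** One AD patient in Paradigm 1 and one bvFTD patient in Paradigm 2 would satisfy both. This is correct: parallel opening within each diagnosis is inferred from the milestones and the shared tDCS window. If groups were filled in sequence, calendar time would be confounded with paradigm, and a stated rule would still be needed.
- **Much of the 56.2% comes from analysing raw scores.** Change scores bring it to about 5% in that scenario. This is also correct, but change scores reject in about 13% at 1.0 SD in the other scenario.
- **Bias is possible, not shown.** The documents do not say allocation is non-random, and some front matter could not be checked. This stands.

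**Conclusion.** The point holds and should be fixed. Two groups with the same eligibility are formed by an undescribed process and then compared without baseline adjustment. Under the assumed differences of 0.25 to 1.0 SD, the false-positive rate of the raw test at 10 v 10 is between about 7% and 56%, depending on the size of the difference and on how it carries forward. Those differences and the 0.7 correlation are assumptions, so the figures show sensitivity and do not estimate bias in this trial. The damage is limited to the comparison of paradigms.

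Even a randomised difference could not be attributed to polarity alone. For AD, Paradigm 1 means that "DMN connectivity will be stimulated in AD patients through anodal tDCS of the posterior DMN", whereas Paradigm 2 is cathodal and targets the anterior SN, so polarity and site change together. The same holds in mirror image for bvFTD.

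**What to change.** 1. In Aims 1 and 2, state that each eligible patient is randomised 1:1 to Paradigm 1 or Paradigm 2 within diagnosis. Use a concealed permuted-block list held by someone who does not enrol patients. Randomise replacements for drop-outs, and patients from the additional centres foreseen in section B.f, in the same way.
2. In Statistical analysis, replace the raw t-test between paradigms with ANCOVA within each diagnosis, with the T1 score (and separately the T2 score) as outcome and the T0 score as covariate. Name in advance the scores to be compared.
3. State that any difference is between whole paradigms, with polarity and site together.
4. If allocation remains non-random, describe how it is done and label the comparison exploratory.

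**Cost.** One randomisation list, a short amendment and one changed sentence in the statistics section. There are no extra patients or visits: the total stays at 40, with 10 per group, and T0 scores are already collected. Staff lose the choice of paradigm, both paradigms must be open to each diagnosis at the same time, and ANCOVA uses one degree of freedom (17 left instead of 18).
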